8. ANALYSIS DETAILS

The results of the analyses will be reported following the principles of the ICH E3 guidelines on the Structure and Content of Clinical Study Reports.

8.1 Recruitment and follow-up patterns

- Recruitment by site
- Withdrawals by site
- Mortality 1, 2 and 5 years post randomisation

Doc No: ST06-RD01 Page **17** of **35**

Doc No: ST06-RD01 Page **18** of **35**

8.3 Baseline Characteristics

- Age, mean (SD) by treatment arm
- Gender, no. (%) by treatment arm
- Dependency prior to hospital admission, no. (%) by treatment arm
- Height (cm), mean (SD) by treatment arm
- Predicted body weight (kg), mean (SD) by treatment arm
- Admission diagnostic category, no. (%) by treatment arm
- Presence of ARDS, no. (%)by treatment arm
- Aetiology of Ards, no. (%) by treatment arm
- APACHE II score, mean (SD) by treatment arm
- Arterial blood gas PaCO₂, mean (SD) by treatment arm
- PaO₂/FiO₂ ratio closest to but prior to randomisation, mean (SD) by treatment arm
- Second qualifying PaO₂/FiO₂ ratio, mean (SD) by treatment arm
- Worst PaO₂/FiO₂ ratio, mean (SD) by treatment arm
- Arterial pH, mean (SD) by treatment arm
- Total SOFA score, mean (SD) by treatment arm
- Mode of ventilation, no. (%) by treatment arm
- Use of Adjunctive therapies, no. (%) by treatment arm
- Mean airway pressure (cmH₂O), mean (SD) by treatment arm
- PEEP (cmH₂O), mean (SD) by treatment arm
- Plateau Pressure (cmH₂O), mean (SD) by treatment arm
- Total Respiratory Rate (breaths/min), mean (SD) by treatment arm
- Minute Volume (L/min), mean (SD) by treatment arm
- Tidal Volume (ml/kg PBW), mean (SD) by treatment arm

8.4 Trial treatment

- Treatment allocation (Intervention), no. (%) commencing ECCO₂R
- Adherence to protocol-specified intervention, no. (%) by treatment arm receiving
 ECCO₂R for >48 hrs
- Duration of ECCO₂R mean(SD) days

Doc No: ST06-RD01 Page **19** of **35**

8.5 Trial Outcomes

- All-cause mortality 90 days after randomisation, no (%) by treatment arm, Risk ratio 95%
- Tidal Volume (ml/kg PBW) at days 2 and 3 after randomisation, mean (SD) by treatment arm, difference in mean with 95% CI
- Ventilator free days at 28 days after randomisation, mean (SD) by treatment arm,
 difference in mean with 95% CI
- Ventilation duration in survivors after randomisation at 28 days, mean (SD) by treatment arm, difference in mean with 95% CI
- Need for ECMO up to day 7, no (%) by treatment arm, Risk ratio 95% CI
- Mortality rate at 28 days after randomisation, no (%) by treatment arm, Risk ratio 95%
- Mortality rate at 6 months after randomisation, no (%) by treatment arm, Risk ratio 95%
- Mortality rate at 1 year after randomisation, no (%) by treatment arm, Risk ratio 95% CI
- SGRQ at 1 year after randomisation, Symptoms score, Activity score, Impacts score and
 Total score mean (SD) by treatment arm, difference in mean with 95% CI
- Need for home oxygen at 6 months and 1 year after randomisation, no (%) by treatment arm, Risk ratio 95% CI
- Post Traumatic Stress Syndrome Questionnaire (PTSS-14) at 1 year after randomisation,
 mean (SD) by treatment arm, difference in mean with 95% CI
- Montreal Cognitive Assessment (MoCA-BLIND) or AD8 Dementia Screening Interview (AD8) at 1 year after randomisation, mean (SD) by treatment arm, difference in mean with 95% CI
- Right heart function as determined by echocardiography during 6ml/kg PBW and
 ≤3ml/kg PBW tidal volume ventilation. Echocardiography parameters including but not
 limited to ventricular size and function and TAPSE, mean (SD) by treatment arm,
 difference in mean with 95% CI

Doc No: ST06-RD01 Page **20** of **35**

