2.2 Secondary outcome measures

- I. Tidal volume (ml/kg PBW) at day 2 and day 3 after randomisation
- II. Ventilator free days at 28 days after randomisation
- III. Duration of ventilation in survivors after randomisation at 28 days
- IV. Need for ECMO up to Day 7
- V. Mortality rate at 28 days, 6 months and 1 year after randomisation
- VI. Health Related Quality of Life (HRQoL) at 6 months and 1 year after randomisation
- VII. Adverse event rate
- VIII. Health & Social Care Service costs at 6 months and 1 year
 - IX. St George's Respiratory Questionnaire (SGRQ) at 1 year and need for home oxygen at 6 months and 1 year after randomisation
 - X. Post Traumatic Stress Syndrome Questionnaire (PTSS-14) at 1 year after randomisation
- XI. Montreal Cognitive Assessment (MoCA-BLIND) or AD8 Dementia Screening Interview (AD8) at 1 year after randomisation

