3.3 Data completion schedule

Study Visits and Procedures

Clinical data will be collected during trial participants stay in the ICU up to 28 days after randomisation. For routinely collected clinical data the NHS record will be the source document and for study specific clinical measurements the CRF will be the source document.

Day 0 (baseline)

Day 0 is 24 hours prior to randomisation. If more than one value is available for this 24-hour period, the value closest but prior to the time of randomisation will be recorded. Day 0 (baseline) data collected will include but is not limited to:

- Patient demographics (date of birth, gender, measured height)
- ICNARC Case Mix Programme (CMP) number
- Scottish Intensive Care Society Audit Group (SICSAG) number
- Date/time of consent and randomisation
- Date and time of ICU admission
- Admission diagnostic category
- Assessment of functional status
- Presence of Acute Respiratory Distress Syndrome (ARDS) and aetiology
- Date/time of onset of mechanical ventilation
- The Acute Physiology and Chronic Health Evaluation score (APACHE II)

Doc No: ST06-RD01 Page **10** of **35**

- PaO₂/FiO₂ ratio (Qualifying PaO₂ /FiO₂ ratios including date/time)
- Date and time of worst PaO₂/FiO₂ ratio
- Determinants of Sequential Organ Failure Assessment (SOFA) score
- Ventilation parameters including but not limited to: Mode of ventilation, minute volume, RR, mean airway pressure, plateau pressure, PEEP
- Arterial blood gas including but not limited to FiO₂, PaO₂, PaCO₂, pH
- Date/time onset of ECCO₂R therapy (from commencement of CO₂ removal)
- Use of adjunctive therapies including Neuromuscular Blocking Drugs (NMBD) and prone position
- Echocardiography parameters including but not limited to ventricular size and function and tricuspid annular plane systolic excursion (TAPSE)

Daily Data:

Day 1 is from the time of randomisation to the end of that calendar day. If more than one value is available for this period, the value closest but after the time of randomisation will be recorded. All other daily measurements will be recorded and collected between 6-10am or as close to this time as possible, unless otherwise stated in the CRF. Daily data will be collected to day 7 and will include but is not limited to:

- Ventilation parameters including but not limited to: Mode of ventilation, minute volume, RR, mean airway pressure, plateau pressure, PEEP
- Arterial blood gas including but not limited to FiO₂, PaO₂, PaCO₂, pH

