3.5 Data coding

The variable codings will be as specified on the CRF.

4. **DEFINITION OF TERMS**

Term	Definition
Discharge from	First discharge to a medical ward in the hospital or another hospital;
critical care	a transfer between ICUs is not considered a discharge from critical
	care.
Hospital discharge	Hospital discharge is the first date that the patient is discharged to
	home/ community, a transfer between hospitals is not considered
	as a hospital discharge
Unassisted	Extubated with supplemental oxygen, or room air, or open T-tube
breathing i.e. no	breathing, or tracheostomy mask breathing, or CPAP \leq 5 cm H ₂ O
ventilatory support	without pressure support for a calendar day. Patients receiving
	pressure support via non-invasive ventilation will be defined as
	receiving ventilatory support (except for sleep disordered
	breathing).
VFDs to day 28	The number of days from the time of initiating unassisted breathing
	to day 28 after randomisation, assuming survival for at least two
	consecutive calendar days after initiating unassisted breathing and
	continued unassisted breathing to day 28. If a patient returns to
	assisted breathing and subsequently achieves unassisted breathing

Doc No: ST06-RD01 Page **13** of **35** to day 28, VFDs will be counted from the end of the last period of assisted breathing to day 28. A period of assisted breathing lasting less than 24 hours and for the purpose of a surgical procedure will not count against the VFD calculation. If a patient was receiving assisted breathing at day 27 or dies prior to day 28, VFDs will be zero. Patients transferred to another hospital or other health care facility will be followed to day 28 to assess this endpoint.

Duration of ventilation

Counted from recruitment to the end of the last period of assisted breathing

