7. ANALYSIS PRINCIPLES

The primary analysis will be conducted on all outcome data obtained from all participants as randomised and regardless of protocol adherence, i.e. intention to treat analysis.

Standard approaches will be used to detect patterns in missing data. Baseline characteristics, follow-up measurements and safety data will be described using the appropriate descriptive summary measures depending on the scale of measurement.

For the primary outcome and other dichotomous outcomes, risk ratios and 95% confidence interval (CI) will be calculated. The primary outcome of 90 day mortality will be analysed using chi-square and a secondary analysis using logistic regression to adjust for age, SOFA score, Baseline PaO_2 / FiO_2 and Baseline Plateau Pressure will also be carried out. The comparison of continuous outcomes between the two groups will be investigated using analysis of variance/analysis of covariance (if baseline measurements available), adjusting for other covariates where appropriate. Time-to-event outcomes will be analysed by survival methods and reported as hazard ratios with 95% CI. The intention-to-treat basis analysis will use a significance level of <0.05 for the primary outcome. Sensitivity analysis will be performed for the primary outcome excluding the first two intervention arm patients at each site in order to address potential learning effects. This would be explored further using a power curve model.

Doc No: ST06-RD01 Page **16** of **35**

Per protocol analysis will also be carried out for the secondary outcome of Tidal Volume at Days 2 and 3 i.e. including those who were on VV-ECCO₂R on day 2 and 3 in the intervention arm. Estimates of effects/association and 95% CI will be reported for secondary and exploratory outcomes.

An independent statistician (for the DMEC) will conduct an interim analysis for the primary outcome measure before the recruitment of 560 patients. Using the chi-square statistic (mortality by treatment group), a p value less than 0.001 will be used according to the Haybittle-Peto stopping rule.

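### Mean ventilation duration is compared between arms in survivors only, which is not a randomised comparison, and its 28-day horizon is not defined

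*SAP*

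**What the plan says.** Item III of SAP section 2.2 is "Duration of ventilation in survivors after randomisation at 28 days". Section 8.5 sets the summary, "Ventilation duration in survivors after randomisation at 28 days, mean (SD) by treatment arm", and the effect measure, a difference in means with its 95% CI. Section 7 gives the method for outcomes of this type: "The comparison of continuous outcomes between the two groups will be investigated using analysis of variance/analysis of covariance".

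The draft outcome table in Appendix 3 has rows for ventilation duration in all patients, survivors and non-survivors. Its columns include a difference with 95% CI and a p-value. The survivor row is therefore laid out as a between-arm comparison, not only as description.

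Section 4 defines duration of ventilation as "Counted from recruitment to the end of the last period of assisted breathing". That definition has no cap at day 28 and no rule for a patient still ventilated then. Section 3.3 states: "Clinical data will be collected during trial participants stay in the ICU up to 28 days after randomisation". The same section lists the dates of ventilation discontinuation and of death among the items collected, without attaching a day-28 limit to them.

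Two other provisions bear on the point. Section 7 says "Time-to-event outcomes will be analysed by survival methods and reported as hazard ratios with 95% CI", but the SAP does not assign ventilation duration to that class. Ventilator-free days (VFDs) are a separate secondary outcome in which death is counted: "If a patient was receiving assisted breathing at day 27 or dies prior to day 28, VFDs will be zero".

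**The concern.** The primary hypothesis in section 1 is that ECCO2R with lower tidal volumes reduces mortality. If it does, the ECCO2R survivors include patients who would have died under standard care, and the control survivors include no such patients. The two survivor groups then differ in composition because of treatment. A difference in their mean duration mixes any effect on ventilation with that change in composition. The as-randomised principle in section 7 is lost for this outcome.

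The outcome serves secondary objective ii, duration of mechanical ventilation. If the patients saved are ventilated longer than other survivors, a treatment that saves lives and leaves everyone else's ventilation unchanged would appear to prolong ventilation.

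A second problem is that the phrase *at 28 days* can be read in two ways: it may say who counts as a survivor, or when counting stops. Two analysts could follow the SAP and report different numbers.

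**Working it through.** **Inputs from the SAP (section 5):** control mortality 41%; 23% relative reduction, stated as 9 points absolute; 90% power; p value 0.05 (taken as two-sided); 3% dropout; 560 per group. These are 90-day figures. The SAP gives no planning value for day-28 mortality, so they stand in for it.

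**Assumed, because the SAP gives no ventilation durations:** the durations used below, and that ECCO2R causes no death in a patient who would survive on standard care.

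**1. Check of the mortality inputs.** With 0.41 against 0.41 × 0.77 = 0.3157, 90% power, two-sided 0.05 and no continuity correction, the two-proportion formula gives 545 per arm. Then 545 / 0.97 = 562 per arm, 1,124 in total, which agrees with the stated 560 and 1,120 to within rounding. (With the rounded 9 points, 0.32, it gives 600, then 619 per arm.) The 80% power statement also reproduces: 0.41 against 0.328 gives 543, then 560 per arm.

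**2. Share of ECCO2R survivors with no counterpart in control.** Control survival is 0.59 and ECCO2R survival is 0.59 + 0.09 = 0.68. The share is 0.09 / 0.68 = 13.2%. With the 8-point reduction that the SAP also mentions, it is 0.08 / 0.67 = 11.9%.

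**3. Shift in the survivor mean.** Let *d* be the mean duration in saved patients minus that in patients who survive under either arm. With no treatment effect on duration in the latter group, the shift is 0.09 / 0.68 × *d*.

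| *d* (days, assumed) | Shift in ECCO2R survivor mean (days) |
|---|---|
| −5 | −0.66 |
| 0 | 0 |
| +3 | +0.40 |
| +5 | +0.66 |
| +10 | +1.32 |

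**4. Effect of a cap at day 28.** Durations were simulated as gamma variables with coefficient of variation 0.8 and a mean of 12 days in patients who survive either way. Survivors with data number about 560 × 0.59 × 0.97 = 320 in control and 560 × 0.68 × 0.97 = 369 on ECCO2R. VFDs were taken as 28 minus the capped duration in survivors and zero in deaths.

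| Mean in saved patients (days) | Shift, uncapped | Shift, capped at day 28 | Chance of a nominally significant longer duration (capped) | Difference in mean VFDs |
|---|---|---|---|---|
| 20 | +1.06 | +0.67 | 19% | +1.04 |
| 25 | +1.72 | +0.94 | 33% | +0.85 |
| 30 | +2.38 | +1.15 | 45% | +0.71 |

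The cap reduces the shift in each scenario; the restriction to survivors is what produces it. In the same scenarios VFDs favour ECCO2R while survivor duration favours control. Both outcomes bear on objective ii, and the SAP has no rule for reading such a conflict.

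**5. Start of the clock.** Section 4 counts from recruitment; sections 2.2 and 8.5 and the Appendix 3 table count from randomisation. The footnote to the inclusion criteria separates the window to consent from a further 8 to 24 hours to randomise and start the intervention, so the two times need not coincide.

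**The case against.** The strongest reply is that the outcome does limited harm where it stands. It is one of eleven listed secondary outcomes, beside primary mortality, 28-day mortality and VFDs. The draft table also shows rows for all patients and non-survivors, and section 7 sets a significance level for the primary outcome only. This limits the consequence but does not supply the missing comparison. VFDs combine death with duration by design. The row for all patients lets an early death count as short ventilation. The p-value column still invites a test of the survivor row.

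Four stronger readings are tempting, and the SAP does not support them:

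- *Duration is truncated at day 28, and this creates the apparent prolongation.* Section 4 has no cap, so truncation is only one possible reading, and in the simulations it shrank the shift.
- *Patients still ventilated at day 28 have no observed end date.* Section 3.3 lists the date of ventilation discontinuation with no day-28 limit, although ICU clinical data stop at day 28. The document is ambiguous on this; it does not show that the date is missing.
- *The comparison will mislead in the wrong direction if the hypothesis is true.* That needs saved patients to be ventilated longer, which the SAP nowhere states. The shift is zero or negative otherwise, and a real shortening of ventilation would offset it.
- *The recruitment/randomisation mismatch biases the comparison.* An interval before randomisation is equal between arms on average, so this is a slip in wording.

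It is also fair to say that a subdistribution hazard ratio does not isolate duration from death. It is offered because it keeps all randomised patients and shows both events, not because it answers a pure duration question.

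**Conclusion.** The point holds as a cheap improvement to one secondary outcome; the primary analysis is untouched. The planned difference in survivor means conditions on an event that treatment is expected to change, and its horizon and survivor definition are not fixed. On the SAP's own planning figures about 13% of ECCO2R survivors would have no control counterpart. A shift of about 0.4 to 1.3 days follows if they are ventilated 3 to 10 days longer, before any cap at day 28.

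The 13% rests on 90-day mortality standing in for day 28 and on treatment causing no deaths among patients who would otherwise survive. The size and sign of the shift, and the 19% to 45% chances, rest on assumed durations. That survivors are not a randomised comparison when treatment changes mortality does not depend on those durations.

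**What to change.** - **Descriptive rows.** Keep the survivor and non-survivor means, labelled descriptive and without a p-value. State the day at which survival is judged, the day at which counting stops, and how a patient still ventilated on that day is handled.
- **Added analysis.** In all randomised patients, analyse time from randomisation to sustained unassisted breathing, with death as a competing event and administrative censoring at day 28. Report the cumulative incidence of unassisted breathing and of death by arm, with a between-arm estimate and 95% CI, for example a subdistribution hazard ratio. Define *sustained*, including how a death after unassisted breathing but before day 28 is coded. The section 4 rules for unassisted breathing and VFDs are a starting point.
- **Reading.** Say that this result is to be read together with 28-day mortality, because it does not separate duration from death.
- **Clock.** Replace recruitment with randomisation in the section 4 definition.

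The cost is SAP wording and one extra model. Section 3.3 already lists the dates of ventilation discontinuation and of death. The downside is an effect measure less simple than a difference in mean days.

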8.6 Toxicity/ Symptoms

• Adverse Event Rate, no. events (%) by treatment arm , no. patients (%) by treatment arm. Risk Ratio and 95% CI.

AEs of interest are as follows:

Device failure causing AE Haemolysis Bleeding

At cannula site

Other site

Infectious complications

Heparin induced thrombocytopenia

- Adverse Device Effect, no. events (%) by treatment arm, no. patients (%) by treatment arm. Risk Ratio and 95% CI.
- Serious Adverse Event, no. events (%) by treatment arm and System Organ Class, no.
 patients (%) by treatment arm. Risk Ratio and 95% CI.
- Serious Adverse Device Effect, no. events (%) by treatment arm and System Organ Class, no. patients (%) by treatment arm. Risk Ratio and 95% CI.
- Unanticipated Serious Adverse Device effect, no. events (%) by treatment arm and
 System Organ Class, no. patients (%) by treatment arm. Risk Ratio and 95% CI.

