Treatment		
Process		
Other		

^{*}Mean (SD) no. of days on ECCO₂R

Doc No: ST06-RD01 Page **28** of **35**

Table x.x.x Main Clinical Outcome variables

	ECCO₂R Intervention n = (%)	Standard Care n = (%)	Difference (95% CI)	p-value
Primary outcome; Mortality 90 days				
post randomisation#				
VFDs 28 days post randomisation				
Ventilation duration post				
randomisation				
All				
Survivors				
Non-survivors				
Need for ECMO to day 7				
Yes				
No [#]				
Mortality rate at 28 days post				
randomisation [#]				
Mortality rate at 6 months post				
randomisation [#]				
Mortality rate at 1 year post				
randomisation [#]				
SGRQ				
Symptoms Score				
Activity Score				
 Impacts Score 				
Total Score				
Need for home oxygen at 1 year post				
randomisation#				
PTSS-14 Score				
MoCA-Blind				
AD8 Dementia Screening				

Mean (SD) presented for treatment arms

Figure x.x.x. Kaplan Meier Curve

Time to death and no. of deaths on x-axis

Doc No: ST06-RD01 Page **29** of **35**

^{*}No. (%) for treatment arms and Risk Ratio and 95% CI presented

Table x.x.x. Tidal Volume after Randomisation

	ECCO₂R Intervention n = (%)	Standard Care n = (%)	Mean Difference (95% CI)
Tidal volume ml/kg PBW			
Day 2			
Day 3			
Day 4			
Day 5			
Day 6			
Day 7			
Tidal volume ml/kg PBW*			
Day 2			
Day 3			

Mean (SD) and Min/Max presented for TV and no. (total % out of 40) for recruitment rate.

Doc No: ST06-RD01 Page **30** of **35**

^{*}Per protocol population i.e. those who were on VV-ECCO₂R on day 2 and 3 in the intervention arm

Table x.x.x. Safety by Treatment Group

		Number of events			Number of patients			
		Total n	Intervention ECCO ₂ R n (%)	Standard Care n (%)	Total n (%)	Intervention ECCO ₂ R n (%)	Standard Care n (%)	RR(95%CI)
AEs, SAEs, ADE, SADE, USADE	Total SAEs							
	Related to study device							
	Related to study device and unanticipated							
	Total AEs							
	Related to study device							
SAEs	Cardiac Disorders							
	Hepatobiliary disorders							
	Respiratory, thoracic and mediastinal disorders							
	etc							
AEs	Device failure causing AE							
	Haemolysis							
	Bleeding at cannula site							
	Bleeding at other site							
	Infectious complications							
	Heparin induced thrombocytopenia							
Adverse Device effect								
Serious Adverse Device effect								

The REST Trial STATISTICAL PLAN (Final version 1.0, 16/12/19)

Unanticipated				
Serious Adverse				
Device effect				

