For no. of events %s are calculated within total SAEs, AEs, ADEs and SADEs respectively within treatment arm.

Doc No: ST06-RD01 Page **32** of **35**

Table xxx. Follow-up Questionnaires at 1 year

	ECCO₂R Intervention n = (%)	Standard Care n = (%)	Difference (95% CI)
Saint Georges			
Questionnaire			
PTSS-14			
MoCA			
AD8			

Figure x.x.x. Subgroup Analyses

OR and 99% CI will be presented graphically alongside the n(%) for interaction terms for the following pre-specified subgroups

	Treatment Group			
	Intervention ECCO ₂ R	Standard Care	Difference (99% CI)	
Presence of ARDS prior to randomisation				
Yes				
No				
Baseline PaO ₂ /FiO ₂ ratio prior to randomisation				
<50				
50-99				
100-150				
Baseline Plateau Pressure prior to randomisation				
Quartile 1				
Quartile 2				
Quartile 3				
Quartile 4				
Volume of ECCO₂R participants at center				
<10 cases				
>=10 cases				

Doc No: ST06-RD01 Page **33** of **35**

The REST Trial STATISTICAL PLAN (Final version 1.0, 16/12/19)

	Treatment Group		
	Intervention ECCO ₂ R	Standard Care	Difference (99% CI)
Vasopressor requirement prior to randomisation			
Yes			
No			
Baseline PaCO ₂ prior to randomisation			
Quartile 1			
Quartile 2			
Quartile 3			
Quartile 4			
Duration of Carbon Dioxide (CO ₂) removal			
Quartile 1			
Quartile 2			
Quartile 3			
Quartile 4			
Baseline driving pressure prior to randomisation			
Quartile 1			
Quartile 2			
Quartile 3			
Quartile 4			
Baseline risk of death score (Apache II) quintiles prior to			
randomisation			
Quintile 1			
Quintile 2			
Quintile 3			
Quintile 4			
Quintile 5			

Table x.x.x. Exploratory Outcome Measures

	Treatment Group		
	Intervention ECCO₂R	Standard Care	Difference (99% CI)
Baseline / Day 0:			
 Tricuspid annular plane systolic excursion (TAPSE) measured in cm Right ventricular strain (RVS) measured in percentage Right ventricle fractional area of change (FAC) measured in percentage Right ventricle end diastolic area to Left ventricle end diastolic ratio (EDA ratio) measure as a ratio (e.g. 0.6) Left ventricular end diastolic diameter measured in cm Left ventricle function measured in percentage 			
Day 1 or 2:			
 TAPSE measured in cm RVS measured in percentage Right Ventricle FAC measured in percentage Right ventricle EDA ratio Left ventricle end diastolic diameter measured in cm Left ventricle function measured in percentage 			

Doc No: ST06-RD01 Page **35** of **35**

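### Risk ratios are planned for device effects that standard-care patients are hardly expected to have, and event percentages use each arm's own events as denominator, so neither measures the burden of harm

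*SAP*

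**What the plan says.** SAP section 8.6 uses one template for all safety outcomes. For device effects it plans "Adverse Device Effect, no. events (%) by treatment arm, no. patients (%) by treatment arm. Risk Ratio and 95% CI". For serious device effects it plans "Serious Adverse Device Effect, no. events (%) by treatment arm and System Organ Class, no. patients (%) by treatment arm. Risk Ratio and 95% CI". The unanticipated class begins "Unanticipated Serious Adverse Device effect, no. events (%) by treatment arm and" and ends with the same risk ratio and interval.

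The template is also applied to general harms. For AEs the plan is "Adverse Event Rate, no. events (%) by treatment arm , no. patients (%) by treatment arm. Risk Ratio and 95% CI", and the SAE line starts "Serious Adverse Event, no. events (%) by treatment arm and System Organ Class, no" and continues in the same way.

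The draft safety table in Appendix 3 has a block for events and a block for patients, with a column for the risk ratio and its interval. Some rows are labelled "Related to study device". The footnote reads: "For no. of events %s are calculated within total SAEs, AEs, ADEs and SADEs respectively within treatment arm".

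Section 6.1 allocates patients 1:1 to ECCO₂R with lower tidal volume ventilation or to standard care. Section 1.2 makes safety a secondary objective, and section 2.2 lists the adverse event rate as a secondary outcome.

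**The concern.** There are two separate faults.

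**Device effects.** An event counts as a device effect because it is attributed to the study device. Patients allocated standard care are not meant to receive that device, so their expected count is about zero. A risk ratio then has a zero denominator. The SAP gives no rule for this case, so the cell stays empty or the analyst chooses a correction after seeing the data.

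**Event percentages.** A percentage of the arm's own events describes the mix of events. It says nothing about how many events each patient had. Two arms with very different burdens can show the same percentage, and two arms with equal counts can show different ones. In this form the percentage cannot express an adverse event rate.

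This is an invasive device trial whose safety findings will be weighed against a hoped-for 9-point absolute reduction in mortality. For three named safety outcomes the planned comparison fails, and the event percentages can mislead a reader who takes them as rates.

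**Working it through.** **Inputs.** From the SAP: 1:1 allocation (section 6.1) and 560 patients per group (section 5). The 560 serves only as a denominator. It follows from 41% against 0.77 × 41% = 31.57% at 90% power and two-sided 5% (two-sidedness assumed): 545 per arm, and 545/0.97 ≈ 562, close to the stated 560. The SAP states no safety rates, so there is no safety figure to reproduce. **All safety counts below are assumptions for illustration.**

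**1. Risk ratio with no control events.** RR = (a/n₁)/(b/n₂). With b = 0 it is undefined for every a > 0. Adding a constant c to each cell gives

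RR = [(a + c)/(n₁ + 2c)] / [c/(n₂ + 2c)], which is (a + c)/c when n₁ = n₂.

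The 95% CI is exp(log RR ± 1.96 × SE), with SE² = 1/(a + c) − 1/(n₁ + 2c) + 1/c − 1/(n₂ + 2c).

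For a = 28 and b = 0:
- c = 0.5: RR = 28.5/0.5 = 57, SE 1.425, CI 3.5 to 931.
- c = 0.1: RR = 28.1/0.1 = 281, SE 3.167, CI 0.6 to about 140,000.

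The data are the same, but the estimate changes about fivefold and the interval moves from excluding 1 to including it.

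| Assumed ECCO₂R patients with a device effect (of 560; controls 0) | RR, c = 0.5 (95% CI) | RR, c = 0.1 | Incidence | Exact 95% CI |
|---|---|---|---|---|
| 6 | 13 (0.7 to 230) | 61 | 1.1% | 0.4 to 2.3% |
| 28 | 57 (3.5 to 931) | 281 | 5.0% | 3.3 to 7.1% |
| 56 | 113 (7.0 to 1824) | 561 | 10.0% | 7.6 to 12.8% |
| 112 | 225 (14 to 3611) | 1121 | 20.0% | 16.8 to 23.6% |

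The exact limits are Clopper–Pearson: the 2.5% quantile of Beta(a, 560 − a + 1) and the 97.5% quantile of Beta(a + 1, 560 − a). Incidence in the ECCO₂R arm needs no correction and is estimable in every row. With no control events it equals the risk difference.

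**2. Event percentages on the footnote's denominator.**
- Assumed bleeding events: 60 among 200 AEs (ECCO₂R) and 30 among 100 (control). The percentages are 60/200 = 30% and 30/100 = 30%. Per 100 patients randomised they are 60/560 = 10.7 and 30/560 = 5.4, a ratio of 2.
- Assumed infectious complications: 40 among 200 and 40 among 100. The percentages are 20% and 40%. Per 100 patients both arms have 40/560 = 7.1.

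The first case hides a doubling. The second shows a difference, against the control arm, that does not exist. By the same rule a total row is 100% in any arm with events, and a control arm with no device effects gives 0/0.

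**3. What the patient-level block can do.** Assumed SAEs in 112/560 and 56/560 patients: RR = 0.20/0.10 = 2.00, SE = √(1/112 − 1/560 + 1/56 − 1/560) = 0.152, 95% CI 1.48 to 2.70. The planned comparison would show a doubling of harm.

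**The case against.** The strongest defence is that the plan already compares harm properly. For AEs and SAEs, section 8.6 and the patient block of the safety table give the number and percentage of patients in each arm with a risk ratio and interval. This stands. A reader might infer from the two faults that excess harm is not measured at all, and the SAP does not support that reading.

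Event counts are printed beside the percentages. Under 1:1 allocation the first bleeding example would appear as 60 (30%) against 30 (30%), so the excess is visible in the counts. This also stands. The percentage adds nothing to those counts and can mislead, but it does not remove them. The footnote belongs to example draft tables, which makes it easy to change, yet it is the only denominator that the SAP states for event percentages.

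For the device rows, only the ratio fails. The planned patient percentage already gives the incidence in the ECCO₂R arm. This is correct, but that incidence has no planned interval.

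A reader might also infer that device effects and cannula-site bleeding cannot occur in controls. That goes too far. Section 8.4 tabulates receipt of ECCO₂R by arm, so off-protocol use is not ruled out. Need for ECMO is counted in both arms, and ECMO involves cannulation, so a control patient can bleed at a cannula site. The SAP lists that event as an AE, and its between-arm comparison should stay.

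**Conclusion.** The point holds as a reporting defect of modest weight. The risk ratios for adverse, serious adverse and unanticipated serious adverse device effects are expected to be non-estimable, or to take their value from an unspecified correction (57 or 281 from the same assumed data). The event percentages show the mix of events, and can look equal when burden differs twofold or differ when burden is equal. The patient-level comparison of AEs and SAEs is valid and can carry the safety conclusion.

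The first part assumes a control count of zero. One or two off-protocol exposures in controls could make the ratio calculable, but it would then rest on those few patients. The SAP does not define a device effect. That definition may sit in the protocol, which was not available, and its absence is not part of this point. The sizes shown are illustrations, because the SAP gives no safety rates.

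**What to change.** 1. In section 8.6, drop the risk ratio for the three device-effect outcomes. Report the number and proportion of ECCO₂R-arm patients with an exact 95% CI. State the denominator: patients allocated to ECCO₂R, and also those who commenced it, since section 8.4 already counts them. List any control-arm occurrence as a count.
2. In the Appendix 3 safety table, replace the own-events percentage with events per 100 patients randomised in each arm, and reword the footnote. The new footnote should also cover unanticipated serious device effects, which the present one does not name.
3. Keep the patient-level percentages and risk ratios for AEs and SAEs, including cannula-site bleeding. A risk difference beside them is optional.

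The cost is a few lines of SAP text, one footnote and the matching table programming. No new data are needed.
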